9.7.1.8.5 ELECTROCARDIOGRAMS

Change from baseline to each postbaseline visit and to the end of treatment in ECG findings (categorized as normal; abnormal, not clinically significant; and abnormal, clinically significant) will be summarized by visit and treatment group using shift tables. Descriptive statistics for ECG parameters and changes from baseline will be presented by treatment cohort.

9.7.1.8.6 OTHER SAFETY ANALYSES

Descriptive statistics for LVEF assessed on echocardiogram or MUGA scans and changes from baseline will be presented by treatment cohort.

9.7.1.9 Extension Phase Analyses

The Extension Phase data will be analyzed separately and described in the SAP.

9.7.2 Determination of Sample Size

Phase 1b – Determination of the Maximum Tolerated Dose

The total number of subjects required for the Phase 1b portion of this study will depend upon the toxicities observed as the study progresses. A sample size of approximately 10 to 30 subjects in Phase 1b will be enrolled to assess MTD. This is not based on statistical power considerations.

Phase 2 – Expansion in Selected Tumor Types

A sample size of 10 evaluable subjects will be enrolled per cohort, with the possibility of expansion to 20 evaluable subjects per cohort, depending on the evaluation by the sponsor and investigators of the efficacy and safety results observed with the initial 10 evaluable

subjects in each cohort. For a reference of the precision of ORR estimates in all cohorts except the EC and the renal cell carcinoma cohorts, the associated 2-sided 95% CIs for the ORR of 10% to 90% for both 10 subjects and 20 subjects, per cohort are provided in Table 10.

The EC cohort may be further expanded to approximately 120 evaluable subjects. The decision to expand enrollment will be based on the results of 2 interim analyses which will spend $\beta=0.012$ and $\beta = 0.024$ at the first and second interim analysis, respectively. Based on an assumption of H_0 : 16% ORR and H_1 : 34% ORR, at 2-sided $\alpha = 0.02$, this design will give 97% statistical power with 120 subjects. At the first interim analysis ($N = 21$), if there are more than 3 responses, then approximately 40 additional subjects will be enrolled. At the second interim analysis ($N = 60$), if there are more than 12 responses, approximately 60 additional subjects will be enrolled. If there are 12 or fewer responses, the sponsor may decide whether to expand enrollment based on clinical outcome, eg, ORR and DOR. If the expansion beyond 60 subjects does not happen, this design for the EC cohort has approximately 86% power at 2-sided $\alpha= 0.02$. The boundaries for the decision to expand enrollment in the endometrial cohort are presented in [Table 11](#).

Table 10 2-sided 95% Confidence Interval for the ORR of 10% to 90% (10 subjects and 20 subjects)

ORR (N=10)	95% CI
10%	(0.003, 0.445)
20%	(0.025, 0.556)
30%	(0.067, 0.653)
40%	(0.122, 0.738)
50%	(0.187, 0.813)
60%	(0.262, 0.878)
70%	(0.348, 0.933)
80%	(0.444, 0.975)
90%	(0.555, 0.998)
ORR (N=20)	95% CI
10%	(0.012, 0.317)
20%	(0.057, 0.437)
30%	(0.119, 0.543)
40%	(0.191, 0.639)
50%	(0.272, 0.728)
60%	(0.361, 0.809)
70%	(0.457, 0.881)
80%	(0.563, 0.943)

Table 10 2-sided 95% Confidence Interval for the ORR of 10% to 90% (10 subjects and 20 subjects)

90%	(0.683, 0.988)
-----	----------------

CI = confidence interval, ORR = objective response rate.

Table 11 Boundaries for the Decision to Expand Enrollment in the Endometrial Carcinoma Cohort

Analysis Number	Cumulative β Spent	Objective Response Rate	P-value
Interim Analysis 1 (N=21)	0.012	0.167	0.93
Interim Analysis 2 (N=60)	0.024	0.204	0.357
Final Analysis (N=120)	0.03	0.238	0.02

As of Amendment 7, the renal cell carcinoma cohort may be further expanded to approximately 145 total evaluable subjects to allow for approximately 100 evaluable subjects who have received 1 or 2 prior therapies that included an anti-PD-1/PD-L1 mAb. The decision to expand enrollment will be based on the results of 2 interim analyses. The first interim analysis will take place when 22 subjects (11 treatment naïve and 11 previously treated without an anti-PD-1/PD-L1 mAb) have sufficient follow-up to be evaluated for response. At the first interim analysis (N = 22), if there are more than 5 responses, then approximately 45 additional subjects will be enrolled. It is anticipated that the additional 45 subjects will consist of approximately 12 treatment naïve subjects enrolled under Amendment 05 and approximately 33 previously treated subjects who have received 1 or 2 prior therapies and have progressed on treatment with an anti-PD-1/PD-L1 mAb. The second interim analysis will include these 45 additional subjects and the 11 treatment naïve subjects included in the first interim analysis and will take place when these 56 subjects have sufficient follow-up to be evaluated for response. [Table 12](#) shows the ORR estimates that are close to the minimum anticipated ORR of about 25% in subjects who had previously failed an anti-PD-1/PD-L1 treatment and about 60% in treatment naïve subjects, and the corresponding 95% CIs in the respective anticipated 33 and 23 subjects for the second interim analysis. At the second interim analysis, whether the previously treated renal cell carcinoma subset will be further expanded will be decided based on clinical review of both efficacy and safety data.

Table 12 Estimate and 2-sided 95% Confidence Interval of the ORR (RCC Subjects for the Second Interim Analysis)

33 subjects who had previously failed an anti-PD-1/PD-L1 therapy		
Number of responses	Observed ORR	95% CI
7	21.2%	(0.090, 0.389)
8	24.2%	(0.111, 0.423)
9	27.3%	(0.133, 0.455)
10	30.3%	(0.156, 0.487)
11	33.3%	(0.180, 0.518)
12	36.4%	(0.204, 0.549)
23 treatment naïve subjects		
Number of responses	Observed ORR	95% CI
13	56.5%	(0.345, 0.768)
14	60.9%	(0.385, 0.803)
15	65.2%	(0.427, 0.836)
16	69.6%	(0.471, 0.868)
17	73.9%	(0.516, 0.898)

CI = confidence interval, ORR = objective response rate, PD-1 = programmed cell death protein, PD-L1 = PD-1 ligand, RCC = renal cell carcinoma.

Table 13 shows the 95% CI for a range of observed ORRs from 25% to 45% in subjects who had previously failed an anti-PD-1/PD-L1 treatment with a sample size of 100 subjects. If the observed ORR is 35%, the sample size of 100 subjects will provide a 95% confidence interval with a lower bound excluding 25%, and this indicates that with 95% confidence the ORR in the combination of lenvatinib and pembrolizumab is greater than 25%.

Table 13 Two-sided 95% Confidence Interval of the ORR, N=100 (RCC Subjects Previously Treated with an Anti-PD-1/PD-L1 mAb)

100 subjects who had previously failed an anti-PD-1/PD-L1 therapy		
Number of responses	Observed ORR	95% CI
25	25.0%	(0.169, 0.347)
30	30.0%	(0.212, 0.400)
35	35.0%	(0.257, 0.452)

40	40.0%	(0.303, 0.503)
45	45.0%	(0.350, 0.553)

CI = confidence interval, mAb = monoclonal antibody, ORR = objective response rate, PD-1 = programmed cell death protein, PD-L1 = PD-1 ligand, RCC = renal cell carcinoma.

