additional subjects will be enrolled. If there are 12 or fewer responses, the sponsor may decide whether to expand enrollment based on clinical outcome, eg, ORR and DOR. If the expansion beyond 60 subjects does not happen, this design for the endometrial carcinoma cohort has approximately 86% power at 2-sided $\alpha= 0.02$. The boundaries for the decision to expand enrollment in the endometrial cohort are presented in Table 2.

Table 2. Boundaries for the Decision to Expand Enrollment in the Endometrial Carcinoma Cohort

Analysis Number	Cumulative β Spent	Objective Response Rate	P-value
Interim Analysis 1 (N=21)	0.012	0.167	0.93
Interim Analysis 2 (N=60)	0.024	0.204	0.357
Final Analysis (N=120)	0.03	0.238	0.02

As of Amendment 6, the renal cell carcinoma cohort may be further expanded to approximately 120 evaluable subjects. The decision to expand enrollment will be based on the results of 2 interim analyses. The first interim analysis will take place when 22 subjects (11 treatment naïve and 11 previously treated without an anti-PD-1/PD-L1 mAb) have sufficient follow-up to be evaluated for response. At the first interim analysis (N = 22), if there are more than 5 responses, then approximately 45 additional subjects will be enrolled. It is anticipated that the additional 45 subjects will consist of approximately 12 treatment naïve subjects enrolled under Amendment 05 and approximately 33 previously treated subjects who have received 1 or 2 prior therapies and have progressed on treatment with an anti-PD-1/PD-L1 mAb. The second interim analysis will include these 45 additional subjects and the 11 treatment naïve subjects included in the first interim analysis and will take place when these 56 subjects have sufficient follow-up to be evaluated for response. [Table 3](#) shows the ORR estimates that are close to the minimum anticipated ORR of about 25% in subjects who had previously failed an anti-PD-1/PD-L1 treatment and about 60% in treatment naïve subjects, and the corresponding 95% CIs in the respective anticipated 33 and 23 subjects for the second interim analysis. At the second interim analysis, whether the previously treated renal cell carcinoma subset will be further expanded will be decided based on clinical review of both efficacy and safety data.

Table 3. Estimate and 2-sided 95% Confidence Interval of the ORR (RCC Subjects for the Second Interim Analysis)

33 subjects who had previously failed an anti-PD-1/PD-L1 therapy		

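### Endometrial cohort: the stated beta spending (0.012/0.024/0.03) and 97% power do not belong to the written expansion rule, whose first look alone loses 4.0% at a true ORR of 34%

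*Protocol*

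**What the plan says.** Protocol 9.7.2 sets H0 at 16% and H1 at 34% ORR, with 2-sided alpha 0.02, and states that "this design will give 97% statistical power with 120 subjects". The expansion decision is "based on the results of 2 interim analyses which will spend" beta of 0.012 and 0.024.

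The rule itself is a count. At N=21, "if there are more than 3 responses, then approximately 40 additional subjects will be enrolled". At N=60, more than 12 responses leads to about 60 further subjects. Discretion is written for this second look only: "If there are 12 or fewer responses, the sponsor may decide whether to expand enrollment based on clinical outcome".

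The text ties the rule to Table 11: "The boundaries for the decision to expand enrollment in the endometrial cohort are presented in" that table. It lists:

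| Look | Cumulative beta | ORR | P-value |
|---|---|---|---|
| N=21 | 0.012 | 0.167 | 0.93 |
| N=60 | 0.024 | 0.204 | 0.357 |
| N=120 | 0.03 | 0.238 | 0.02 |

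The beta values and the 97% recur in the Synopsis (Sample Size Rationale), Protocol 9.7.3, SAP Section 4 and SAP Section 6. SAP Table 2 repeats Table 11 under the title "Boundaries for the Decision to Expand Enrollment in the Endometrial Carcinoma Cohort".

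**The concern.** The Table 11 boundaries agree with the written counts: 0.167 x 21 = 3.5 and 0.204 x 60 = 12.2. The beta and power figures do not agree with those counts. If 3 or fewer responses in 21 means no expansion, the beta spent at that look is the probability of that event at 34%, and a single binomial tail is enough to show that it is well above 0.012.

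EC is the only cohort with a stated hypothesis, power and beta schedule. A reader is told that the first look carries a 1.2% risk of failing to expand an active cohort, when the written rule carries 4.0%. The stated power is also one that the written design does not have.

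**Working it through.** **Inputs** (Protocol 9.7.2 and Table 11): p0 = 0.16, p1 = 0.34; looks at 21, 60 and 120; expand on 4 or more of 21, then on 13 or more of 60; final success at ORR 0.238, and since 0.238 x 120 = 28.56, that is 29 or more of 120. The text says approximately 40 more after 21; I take the second look at exactly 60, as Table 11 does.

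**1. Reproducing the printed figures.** The Table 11 P-values are two-sided, from z = (ORR - 0.16)/sqrt(0.16 x 0.84/N). They come to 0.930, 0.353 and 0.020. The middle value is 0.358 at ORR 0.2035, so its difference from 0.357 is rounding.

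The betas come out of a normal approximation with variance 0.34 x 0.66/N that stops when the observed ORR is within (boundary - 0.16) of 16% on *either* side. At look 1 that interval is 0.153 to 0.167. With SE = sqrt(0.2244/21) = 0.1034, Phi((0.167 - 0.34)/0.1034) - Phi((0.153 - 0.34)/0.1034) = Phi(-1.674) - Phi(-1.809) = 0.012. Carried through all three looks by numerical convolution, cumulative beta is 0.0118/0.0240/0.0299 and power 97.0%. All the stated figures are matched, but this origin is inferred; neither document states it.

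**2. Why that calculation is not the written rule.** In counts, the stopping regions are:

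- N=21: 21 x (0.153, 0.167) = 3.21 to 3.51, which contains no whole number.
- N=60: 60 x (0.116, 0.204) = 6.96 to 12.24, that is 7 to 12.

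Results of 0 to 3 of 21 and 0 to 6 of 60 therefore count as continuing, whereas the written rule does not expand on them.

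**3. The written rule, first look.** P(X <= 3 | 21, 0.34) = 0.0002 + 0.0018 + 0.0090 + 0.0295 = 0.0405. The ceiling on power is 1 - 0.0405 = 0.9595. The ratio to the stated value is 0.0405/0.012 = 3.4.

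**4. The written rule, all looks.** Exact binomial over the 21/60/120 path at ORR 34%. The last column is the probability of success at ORR 16%.

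| Reading | Cumulative beta | Power | One-sided error |
|---|---|---|---|
| Stated | 0.012/0.024/0.03 | 97% | 0.01 (half of 0.02) |
| Both looks bind | 0.040/0.048/0.053 | 94.7% | 0.0099 |
| N=60 discretionary | 0.040/0.040/0.046 | 95.4% | 0.0111 |
| Only N=60 binds | 0/0.013/0.018 | 98.2% | 0.0113 |
| Neither binds | 0/0/0.008 | 99.2% | 0.0133 |

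The losses by look with both binding are 0.0405, 0.0079 and 0.0041. No row gives the stated schedule.

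**5. Is it the approximation?** No. The same normal approximation with one-sided stops at the printed boundaries gives 0.047/0.055/0.060 and 94.0%, further from the stated values than the exact result.

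**The case against.** The best case for leaving the text alone has four parts.

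- *The printed schedule is coherent.* It reproduces under a two-sided calculation, and the plan does state 2-sided alpha. That is so, but both documents present the schedule as belonging to a one-directional count rule, and for that rule it is wrong.
- *The first look may not bind.* The text says what happens above 3 of 21 and does not state in words that 3 or fewer stops the cohort. The 4.0% loss and the 95.95% ceiling do depend on that reading. If the look does not bind, power is 98.2% or 99.2% and 97% is conservative, but then no beta is spent at N=21 and 0.012 is still wrong.
- *The effect is small and no analysis uses it.* With the N=60 look discretionary, as written, the power gap is 1.6 points. The primary analysis is an ORR estimate with a Clopper-Pearson 95% CI, and the 29-of-120 criterion comes only from Table 11. The Amendment 09 change log also treats the primary endpoint analysis as completed, so no enrolment decision would change. All of this stands, and it limits the weight of the point.
- *The replacement figures are not the whole path either.* Protocol 9.1 asks for at least 3 responders among the first 10. If that were binding, P(X <= 2 | 10, 0.34) = 0.284 would be lost there. Sections 9.7.2 and 9.7.3 word that review more softly. The exact figures therefore cover the looks at 21, 60 and 120 only, and the text should say so.

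**Conclusion.** The concern holds. Under the written rule the first look loses 4.0% at ORR 34%, not 1.2%, and this alone exceeds the stated total beta of 0.03. Power is 94.7% with both looks binding or 95.4% with the N=60 look discretionary, which is 1.6 to 2.3 points below 97%. In the discretionary case the one-sided error is 0.0111, slightly above the 0.01 implied by 2-sided 0.02.

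These figures assume that 3 or fewer of 21 means no expansion, looks at exactly 21, 60 and 120, success at 29 or more of 120, and no loss at the first-10 review. The mismatch does not depend on the first assumption, because no combination of binding and non-binding looks returns the stated schedule. Only the stated operating characteristics are affected. It should be fixed, but it does not threaten the ORR estimate or its interval.

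**What to change.** In the Synopsis, Protocol 9.7.2, Table 11 and 9.7.3, and in SAP Section 4, Table 2 and Section 6:

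1. Replace the beta values and the 97% with the exact figures for the written rule: 0.040/0.048/0.053 and 94.7% (one-sided error 0.0099) if both looks bind, or 0.040/0.040/0.046 and 95.4% (one-sided error 0.0111) if the N=60 look is discretionary.
2. State which looks are treated as binding.
3. State that the review of the first 10 subjects is not included in these figures.

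Optionally, label the 86% as the fixed N=60 figure: 17 or more of 60 gives 85.7%. It does not describe a cohort held at 60 because 12 or fewer responded.

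The cost is restated figures and two sentences, with no new subjects, scans or analyses. The only downside is a stated power about 2 points lower.

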9.7.3 Interim Analysis

The evaluation of efficacy and safety by the sponsor and investigators will occur on the initial 10 evaluable subjects while enrollment is ongoing. Based on the outcome of the evaluation the enrollment could be suspended before enrolling the planned 20 subjects in each cohort.

The EC cohort may be expanded to approximately 120 evaluable subjects. Two interim analyses will take place when 21 and 60 subjects have sufficient follow-up to be evaluated for response. The decision to expand enrollment will be based on the results of the 2 interim analyses, which will spend $\beta = 0.012$ and $\beta = 0.024$ at the first and second interim analyses, respectively. Based on an assumption of H_0 : 16% ORR and H_1 : 34% ORR, at 2-sided $\alpha = 0.02$, this design will give 97% statistical power with 120 subjects. At the first interim analysis ($N = 21$), if there are more than 3 responses, then approximately 40 additional subjects will be enrolled. At the second interim analysis ($N = 60$), if there are more than 12 responses, approximately 60 additional subjects will be enrolled. If there are 12 or fewer responses, the sponsor may decide whether to expand enrollment based on clinical outcome, eg, ORR and DOR. If the expansion beyond 60 subjects does not happen, this design for the EC cohort has approximately 86% power at 2-sided $\alpha = 0.02$.

The renal cell carcinoma cohort may be further expanded to approximately 145 evaluable total RCC subjects to allow for approximately 100 evaluable subjects who have received 1 or 2 prior therapies that included an anti-PD-1/PD-L1 mAb. The decision to expand enrollment will be based on the results of 2 interim analyses. The first interim analysis will take place when 22 subjects (11 treatment naïve and 11 previously treated without an anti-PD-1/PD-L1 therapy) have sufficient follow-up to be evaluated for response. At the first interim analysis ($N = 22$), if there are more than 5 responses, then approximately 45 additional subjects will be enrolled. It is anticipated that the additional 45 subjects will consist of approximately 12 treatment naïve subjects enrolled under Amendment 05 and approximately 33 previously treated subjects who have received 1 or 2 prior therapies and have progressed on treatment with an anti-PD-1/PD-L1 mAb. The second interim analysis will include these 45 additional subjects and the 11 treatment naïve subjects included in the first interim analysis and will take place when these 56 subjects have sufficient follow-up to be evaluated for response. At the second interim analysis, whether the previously treated renal cell carcinoma subset will be further expanded will be decided based on clinical review of both efficacy and safety data.

9.7.4 Other Statistical/Analytical Issues

Not applicable.

9.7.5 Procedure for Revising the Statistical Analysis Plan

If the SAP needs to be revised after the study starts, the sponsor will determine how the revision impacts the study and how the revision should be implemented. The details of the revision will be documented and described in the clinical study report.

11 PROCEDURES AND INSTRUCTIONS (ADMINISTRATIVE PROCEDURES)

11.1 Changes to the Protocol

Any change to the protocol requires a written protocol amendment or administrative change that must be approved by the sponsor before implementation. Amendments specifically affecting the safety of subjects, the scope of the investigation, or the scientific quality of the study require submission to health or regulatory authorities as well as additional approval by the applicable IRBs/IECs. These requirements should in no way prevent any immediate action from being taken by the investigator, or by the sponsor, in the interest of preserving the safety of all subjects included in the study. If the investigator determines that an immediate change to or deviation from the protocol is necessary for safety reasons to eliminate an immediate hazard to the subjects, the sponsor's medical monitor and the IRB/IEC for the site must be notified immediately. The sponsor must notify the health or regulatory authority as required per local regulations.

Protocol amendments that affect only administrative aspects of the study may not require submission to health or regulatory authority or the IRB/IEC, but the health or regulatory authority and IRB/IEC (or if regionally required, the head of the medical institution) should be kept informed of such changes as required by local regulations. In these cases, the sponsor may be required to send a letter to the IRB/IEC and the Competent Authorities (or, if regionally required, the head of the medical institution) detailing such changes.

11.2 Adherence to the Protocol

The investigator will conduct the study in strict accordance with the protocol (refer to ICH E6, Section 4.5).

11.3 Monitoring Procedures

The sponsor's/CRO's CRA will maintain contact with the investigator and designated staff by telephone, letter, or email between study visits. Monitoring visits to each site will be conducted by the assigned CRA as described in the monitoring plan. The investigator (or if regionally required, the head of the medical institution) will allow the CRA to inspect the clinical, laboratory, and pharmacy facilities to assure compliance with GCP and local regulatory requirements. The CRFs and subject's corresponding original medical records (source documents) are to be fully available for review by the sponsor's representatives at regular intervals. These reviews verify adherence to study protocol and data accuracy in accordance with local regulations. All records at the site are subject to inspection by the local auditing agency and to IRB/IEC review.

In accordance with ICH E6, Section 1.52, source documents include, but are not limited to, the following:

- Clinic, office, or hospital charts

- Copies or transcribed health care provider notes that have been certified for accuracy after production
- Recorded data from automated instruments such as IxRS, x-rays, and other imaging reports (eg, sonograms, CT scans, magnetic resonance images, radioactive images, ECGs, rhythm strips, EEGs, polysomnographs, pulmonary function tests) regardless of how these images are stored, including microfiche and photographic negatives
- Pain, quality of life, or medical history questionnaires completed by subjects
- Records of telephone contacts
- Diaries or evaluation checklists
- Drug distribution and accountability logs maintained in pharmacies or by research personnel
- Laboratory results and other laboratory test outputs (eg, urine pregnancy test result documentation and urine dip-sticks)
- Correspondence regarding a study subject's treatment between physicians or memoranda sent to the IRBs/IECs
- CRF components (eg, questionnaires) that are completed directly by subjects and serve as their own source

